or diet only (n=4; paraplegic). Skeletal Muscle Cross-Sectional Area (CSA) was measured with T1-axial MRI at **a) pre** and **b) post-12 week** of NMES-RT. Thigh (28%) and knee extensor muscle CSA (35%) showed remarkable hypertrophy (**Fig 2**). Another study demonstrated the effects of NMES-RT and Testosterone on cardio-metabolic risk factors after SCI. In an open-label randomized clinical trial, we examined the effects of complementary approach of 16 weeks of surface NMES evoked RT and testosterone (TRT+RT) compared to testosterone replacement therapy (TRT) only (2-6 mg) on skeletal muscle size, body composition, and peak torque (muscle quality) in persons with motor complete SCI. Twenty-two individuals with chronic motor complete SCI (ages 18-50 years) were randomly assigned to either TRT+RT (n =11) or TRT (n= 11) for 16 weeks (**Fig3**). In **fig. 3**, we determined the effects of TRT+ NMES-RT on whole thigh muscle CSA and whole thigh absolute muscle CSA after accounting for intramuscular fat. Compared to TRT only, TRT+ RT showed delta increase > 20 cm^2; demonstrating the efficacy of loading the paralyzed muscles in evoking muscle hypertrophy. Effects of NMES-RT with TRT on trabecular bone parameters of distal femur and proximal tibia were also measured. Nine participants with SCI were randomized into TRT+RT group for 16-week intervention. Each participant underwent MRI prior to BL and following the intervention PI. MRI microarchitecture techniques were used to evaluate trabecular bone quality, measured as plate width (PW;  $\mu$ m), trabecular bone thickness (TBTh; mm), trabecular bone spacing (TBSp; mm), and network area (NA; 1/mm) for the right proximal tibia (ProxT) and distal femur (DistF). Mixed models with random effects were used to calculate differences between BL and PI (MD  $\pm$  SE) and were then transformed to effect sizes similar to Cohen's d (d, 95% CI [effect size]). Bar plots for trabecular measures of the distal femur depicting the difference for each measure across the intervention period. Small effect sizes were observed for distal femur TBTh variability, TBSp, and NA. A medium effect size was observed for distal femur TBSp variability. Mean  $\pm$  SE. Bar plots for trabecular measures of the proximal tibia depicting the difference for each measure across the intervention period. A small effect size was observed for proximal tibia PW. Medium effect sizes were observed for ProxT, TBTh, TBSp, TBSp variability, and NA. Mean  $\pm$  SE. Following the intervention, ProxT PW (MD: 30.56  $\pm$  22.52; d: 0.48, -0.21 to 1.17 [small]), TBTh (MD: 0.02  $\pm$  0.01; d: 0.70, 0.01 to 1.39 [medium], and NA (MD: 0.04  $\pm$  0.02; d: 0.64, -0.05 to 1.33 [medium]) all increased from BL measures. In contrast, TBSp (MD: -0.25  $\pm$  0.17; d: -0.52, -1.22 to 0.17 [medium]) decreased from BL. The DistF similarly presented with increases in bone quality from BL for PW (MD: 11.7  $\pm$  42.70; d: 0.10, -0.60 to 0.79 [negligible]), TBTh (MD: 0.01  $\pm$  0.01; d: 0.29, -0.41 to 0.98 [negligible]), and NA (MD: 0.03  $\pm$  10/29/2019). **Fig. 4 & 5:** Due to the exploratory nature of the study on small sample size and short duration, we relied primarily in this trial on measuring the

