investigator or medical provider precludes safe participation in the study and/or increases the risk of infection. A large percentage of patients in the department of VA are males. Should female participants be found, in order to ensure heterogeneity of samples between the two groups, postmenopausal and estrogen deficient females and men undergoing anti-androgen therapy or post orchiectomy, will be excluded. In addition, individuals with stage 3b or higher chronic kidney disease and those likely to have bone loss (age >65), will be excluded due to possible renal osteodystrophy and osteoporosis that may increase the risk of bone fractures from bone loading and ES to muscles. We will also exclude those with AIS C & D as they are already engaging in weight bearing activities which may confound the results of the trial. We have chosen inclusion and exclusion criteria for this study, to optimize homogeneity. Should the outcome be positive, it will be necessary to broaden inclusion criteria for future studies so that the methods can be used in a larger number of individuals with SCI.

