**Pitfalls and Alternatives:** Changes in trabecular bone parameters may be indeterminate because of the smallness and heterogeneity of sample size. We will rely on previous experience to calculate the effect size, and on that basis, adequately power future trials. **Failure to recruit proposed sample size:** The applicant's primary mentor ([name]) successfully conducted similar clinical trials in the past and demonstrated that use of telehealth facilitated recruitment and compliance among Veterans with SCI. Additionally, we may recruit non-Veterans to ensure completion of the study within the proposed timeline. [name] has a dual appointment with VCU and can successfully collaborate with VCU to ensure recruitment of the target sample size.

**Statistical Analyses.** After signing consent, the PI will randomly assign a number from 1-20 to participants using a computer program (nQuery). The order of enrollment will determine the participant's number based on level and duration of injury. Summary of information, including means and SD, frequencies and percentages, for all study variables will be calculated at all-time points. T-tests and Pearson chi-square tests will be used to compare characteristics that may act as confounders, including age, level and time since injury.

**Sample Size Justification:** Being a pilot study, consideration of sample size is just to allow determination and examination of preliminary evidence of efficacy and effect size estimation towards a larger future randomized trial. The proposed sample size of 10 per group is adjudged sufficient to accomplish these goals. Although Julious recommends a sample size of at least 12 per group on the basis that gain in precision for estimates of variance becomes relatively small on reaching a sample size of 12, we are unable to meet that target because of cost of the intervention and testing. Our sample size still allows for adequate accuracy. As shown in **Fig 6**, the gain in precision is still limited with a sample size of 10 per group. Although testing efficacy is not the primary goal, we will have 80% power to detect a standardized mean difference of  $d=0.9$  using an alpha of 0.25 corresponding to a large effect size. Type I error rates larger than 0.05 are often used and recommended for pilot studies where tests of efficacy are not the primary aim.

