**Detailed Strategies for the Recruitment Plan.**

Efforts will be made by the applicant (PI), to implement a successful recruitment plan, and to avoid any source of coercion during the actual process. Twenty Veterans (10 in

intervention group vs. 10 in control group) with motor complete SCI involving C8-T10 and AIS A or B classification, will be recruited to participate in a 9 months trial. The primary goal of this work is to ensure that our procedures are safe and effective for persons with motor complete SCI.

The following timeline will be implemented to meet our recruitment goals. We plan to recruit 20 Veterans/non-Veterans over a 2-year period (24 months). We plan to start participants enrollment in the 1st quarter of year-1 and finish in 1st quarter of year-2 (see recruitment table below). We will continue to collect data and finish analysis by the 4th quarter of year two. This is feasible considering our previous experience recruiting for the parent study. Also, we do not anticipate attrition due to prior established compliance with telehealth home-based study. We plan to offer resistant training to participants on a flexible schedule so as to accommodate their lifestyle, to avoid attrition. Participants will be randomized to either intervention or control group.

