## Recruitment Table:

## Feasibility of recruitment:

There is an emphasis on feasibility of the trial recruitment to ensure we reach our target sample size, especially considering the 9-months commitment requirement for each participant. Below is a step-by-step description of our recruitment strategies to demonstrate feasibility:

- Prior to submission of the current application, 3 participants were already identified and were willing to participate in our preliminary work.
- We will contact every SCI physician, nurse and rehabilitation staff (including those at the Spokes sites) about our ongoing protocol through our weekly clinical rounds, grand rounds, and friendly e-mail reminders.
- We will send an email blast through our secured network to our 13 Spokes sites and encourage them to refer potential participants to our research team.
- We will send electronic flyers and the PI will present at our SCI monthly meetings, PVA monthly meeting, SCI quarterly newsletters, hub and spoke annual conferences, and SCI national Chief teleconference meetings.
- Our SCI&D service has a designated wheelchair van that we have been using on a regular basis for transportation of our participants back and forth during the course of clinical trials, assuming they reside in the Richmond area. This accessible transportation has encouraged several participants to be enrolled in previous VA trials and we plan to use this method too to encourage participation in the proposed trial; they will only need to come to the center at the beginning of the trial, mid-term and at the end of the trial for imaging and blood work.

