### **Limitations and Alternatives:**

- 1)** Those with incomplete SCI (AIS C or D) as they may already be engaging in some weight bearing activities that convey some benefits of bone health, hence may confound the results of the study.
- 2)** Those with marked osteopenia and severe osteoporosis as electrical stimulation and loading to already weakened limbs may increase the risk of sustaining stress fractures.
- 3)** It may be difficult to recruit female Veterans because of limited access as they are fewer in number compared to male Veterans.
- 4)** Ability to recruit and retain the required sample size from current SCI & D registry. However, since the primary mentor had previously recruited and retained almost half of the proposed sample size in the parent study, we anticipate similar success rate.
- 5)** Frequent blood sampling; this procedure has been previously used in IRB approved funded studies without recorded incidence.
- 6)** concerns about **retaining participants** to finish the 9 months study; transportation could be a major impairment to participants' compliance in the SCI population. Fortunately, the study involves limited travel since we are going to use Telehealth (a home-based) approach for the intervention and participants would only be required to travel at enrollment, mid-term and at the conclusion for testing procedures at no financial cost to them. Participants affiliated with the Spokes site can complete these tests at their local VAMC.

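### Current limb loading is treated as a confounder only through AIS grade, so an AIS A/B participant already using NMES, FES or standing can enter either arm and carry on, and in controls this dilutes the contrast

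*Combined protocol and SAP*

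**What the plan says.** The Exclusion Criteria under Research Design and Methods state that the study will "exclude those with AIS C & D as they are already engaging in weight bearing activities which may confound the results of the trial". The Human Subject Section repeats this reason (exclusion item 4), as does Limitations and Alternatives (item 1). In all three places the action is the same: AIS C and D are excluded.

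For AIS A and B, neither set of inclusion and exclusion criteria mentions current or earlier NMES, FES, rowing, standing or other loading. The discretionary exclusions (item 17 in the first list, item 18 in the second) concern safe participation and infection risk. The opening of the second exclusion list removes people whose active medical condition may confound the result, and a training programme is not a medical condition.

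The analysis text does not fill the gap. Statistical Analyses names age, level and time since injury as possible confounders to compare. The Data Analysis Plan adjusts each outcome for its own baseline value only. The Adverse Events section says participants keep their usual care throughout, and sets no rule on outside stimulation or standing.

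On size, the Sample Size Justification states that "The proposed sample size of 10 per group is adjudged sufficient to accomplish these goals", the goals being preliminary evidence of efficacy and estimation of an effect size for a future trial. It claims "80% power to detect a standardized mean difference of" 0.9 at an alpha of 0.25.

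**The concern.** If weight bearing in AIS C and D can confound the results, so can electrically evoked or frame-supported loading in AIS A and B, and there it can also resemble the study intervention. AIS grade is a proxy for walking and standing ability. It does not say whether a person with a motor-complete injury is in a stimulation or standing programme.

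The more serious case is concurrent exposure in controls. A participant assigned to passive movement who also uses NMES, FES or a standing frame at home is no longer a passive control, and the between-arm difference shrinks. Neither randomisation nor baseline adjustment corrects this, because it happens after baseline. With 10 per arm, each such person is 10% of the control group. Without any record of exposure, a small observed difference could not be separated into a weak intervention and a contaminated comparison.

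**Working it through.** **Inputs from the plan.** 10 per group, d = 0.9, alpha 0.25 and 80% power (Sample Size Justification). No attrition is allowed for: "we do not anticipate attrition due to prior established compliance with telehealth home-based study" (Detailed Strategies for the Recruitment Plan).

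**Inputs assumed.** c is the share of controls with outside exposure, and r is how effective that exposure is relative to the study course. The documents give neither. I set r = 1 as an upper bound, show c from 0% to 50%, and leave the SD unchanged.

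**Step 1: reproduce the plan's figure.** For a two-group comparison the noncentrality is d × √(n/2) = 0.9 × √5 = 2.012.
- Normal approximation, two-sided: the critical value is 1.150, so power = Φ(2.012 − 1.150) = 80.6%.
- Noncentral t, 18 df, two-sided: the critical value is 1.189, and power = 79.6%.
- One-sided, the same inputs give about 91%.

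The stated 80% therefore reproduces, and the alpha of 0.25 is two-sided.

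**Step 2: dilution by concurrent exposure in controls.** d_eff = 0.9 × (1 − c × r). With r = 1:

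| Exposed controls | d_eff | Power (t, two-sided 0.25) | n per arm for 80% (normal) |
|---|---|---|---|
| 0 of 10 | 0.90 | 79.6% | 10 |
| 1 of 10 | 0.81 | 73.6% | 13 |
| 2 of 10 | 0.72 | 66.9% | 16 |
| 3 of 10 | 0.63 | 59.7% | 20 |
| 4 of 10 | 0.54 | 52.4% | 28 |
| 5 of 10 | 0.45 | 45.2% | 40 |

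If outside exposure were only half as effective (r = 0.5), two exposed controls would do what one does in the table: 0.9 × (1 − 0.2 × 0.5) = 0.81.

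**Step 3: training completed before entry.** Randomisation balances this in expectation, so the question is chance imbalance. Suppose 4 of the 20 participants had trained before (an assumption). The number falling in one arm is hypergeometric, and a 2–2 split has probability 41.8%. The arms therefore differ by 2 or more with probability 1 − 0.418 = 58%, and all 4 fall in one arm with probability 2 × 0.0433 = 9%. Imbalance is likely, but it can go either way.

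**The case against.** **Direction.** A reader might infer that earlier training also pulls the difference towards zero. The documents do not support that. A previously trained person may be assigned to either arm; a control who loses earlier gains over 9 months of passive movement would widen the difference; and ANCOVA on the baseline score removes part of any carry-over already visible at entry. Outside training in the NMES arm has no fixed direction either. Only concurrent exposure in controls clearly dilutes.

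**Evidence of carry-over.** The Preliminary Study reports "Thigh (28%) and knee extensor muscle CSA (35%) showed remarkable hypertrophy", which might suggest that one earlier course matters a great deal. Those are muscle gains. The increase of more than 20 cm² compares testosterone plus training with testosterone alone. Aim 1 concerns bone, where the same section gives distal femur effects of d = 0.10 (plate width) and 0.29 (thickness) after 16 weeks, both intervals including zero. Proximal tibia effects ran from about 0.5 to 0.7 in size, again with testosterone.

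**Overlap with the group's earlier studies.** Feasibility of recruitment says "3 participants were already identified and were willing to participate in our preliminary work"; it does not say that they trained. The remark that follows from "since the primary mentor had previously recruited and retained almost half of the proposed sample size in the parent study" concerns recruiting success and does not say that those people will return. The earlier NMES-RT arms with stated sizes total 5 + 11 = 16. Even if all 16 were among the more than 298 registry patients at the target level, random sampling would give about 20 × 16/298 ≈ 1 participant. Volunteers may return more often than that, and the telehealth pilot gives no size, so the overlap is possible but not established.

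**History and purpose.** Study Procedures provides a 1-hour history and physical examination, and Sources of Materials a records review, so it would be wrong to say that no history is taken; its training content is simply not specified. The pilot is mainly descriptive. At d = 0.9 the standard error is about √(0.2 + 0.81/40) = 0.47, a 95% half-width of about 0.92, beside which a shift of 0.09 to 0.18 is modest. That limits the urgency. It does not remove the point, because dilution is a bias that the interval does not show, and the estimate is what the next trial will use.

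**Conclusion.** The point stands for current and concurrent exposure. By the plan's own reasoning existing loading matters, yet nothing in either list or in the analysis text stops an AIS A or B person in an NMES, FES or standing programme from entering and continuing, or makes that exposure visible afterwards.

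Under the upper-bound assumption, one exposed control in 10 costs 0.09 in d and about 6 points of power; two cost 0.18 and about 13 points. Both figures rest on an exposure rate and a relative effectiveness that the documents do not give. They show what the gap could do, not what will happen. Earlier, completed training is a secondary issue of noise and chance imbalance, and the text does not support a claim that it systematically hides the effect.

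**What to change.** 1. In both exclusion lists, add people who are currently in a lower-limb NMES, FES or regular loading programme.
2. In the history already taken at screening (Study Procedures), record earlier NMES or FES training and earlier participation in the group's studies.
3. At the 30-day pill-count call already planned for all participants, ask both arms about off-study lower-limb stimulation or loading.
4. In the Data Analysis Plan, report exposure by arm and give the 9-month comparison with and without exposed participants. Present the second as a sensitivity analysis, since dropping people for what they did after randomisation loses the protection of randomisation.

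Whether to set a washout, and of what length, is for the sponsor; the documents give no basis for a figure. Any request to avoid outside stimulation or standing is also for the sponsor, and must be reconciled with the statement that usual care continues.

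The cost is one eligibility line, one history item, one question on an existing call and one extra analysis, plus the loss of a few otherwise eligible candidates from a registry pool the plan puts at more than 298. Items 2 to 4 are worth having even if the exclusion is declined, because exposure cannot be reliably reconstructed afterwards.

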Data from the Department of Veterans Affairs suggest that SCI affects an estimated 46,000 Veterans. With about 18,000 new cases of SCI every year, including a significant number of Veterans, the risk of osteoporosis and fracture is worth addressing. The first 2 weeks of SCI is the most critical for bone loss. Thereafter, progression slows down and stabilizes in 2-5 years and in some cases, far beyond 10 years. It is estimated that 50% -70% of individuals with SCI, will sustain a low impact fracture sometime in their lifetime. The sites commonly affected are the distal femur and proximal tibia. Osteoporosis-related fractures involve significant health care expenditure. The medical cost for managing Veterans with SCI alone in 2016 was estimated at \$30,770 - \$62,563 per Veteran, while cost in the acute phase could go above \$140,000^25. The cost of medical care for Veterans with SCI and osteoporosis-related fractures will naturally therefore, have significant impact on the finances of the VA healthcare system and those of Veterans and their families. It is estimated that health care cost for managing osteoporosis-related fractures, as a whole, will reach \$25 billion by 2025. Treating and preventing osteoporosis in persons with SCI is challenging. Anti-resorptive drugs (bisphosphonate and denosumab) and anabolics (PTH peptides), have been shown to reduce fracture risk at vertebral and hip sites. However, there is no consensus on whether they reduce fracture risk at the femur; the site of greatest relevance for persons with SCI. In contrast to anti-resorptive agents, sclerostin, which inhibits bone formation by up-regulating receptor activator of nuclear factor-kappa B ligand (RANKL) and down-regulating osteoprotegerin (OPG), with a net result of increased bone resorption, is emerging as a therapeutic target. Anti-sclerostin drugs (e.g. romosozumab), have been shown to stimulate bone formation, reduce resorption and ultimately increase BMD. Its use in the SCI population is however still being studied. It is only available in injectable form and has a black box warning for cardiovascular events/death, making it unattractive for use in a population already at high risk of cardiovascular events. Very importantly, electrical stimulation (ES) has been shown to partly reduce BMD loss in the femur if initiated early in SCI and it presents no systemic side effects. Bélanger et al., observed that the distal femur and proximal tibia had almost 30% recovery after 24 weeks of daily one-hour ES

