**Aim 2: To determine the impact of home-based NMES-RT protocol plus oral Vit D compared to passive movement and Vit D supplementation on biomarkers of bone formation and bone resorption in Veterans > 1-year post SCI.** Both groups will also receive 9 months of therapy. We hypothesized that NMES-RT will increase osteoblast activity and decrease bone demineralization compared to passive movements. We plan to measure serum 25(OH)D, PTH, Bone specific alkaline phosphatase ( BALP), Procollagen Type 1 Intact N Terminal Propeptide (P1NP), Hydroxyproline (HYP), Carboxy-terminal Crosslinked Telopeptide of Type 1 collagen (CTX), in participants' blood. The role of bone turnover markers in the evaluation of bone loss in persons with SCI has not been established. In able-bodied persons, serum CTX and serum P1NP are considered the best markers of bone resorption and formation, respectively. Blood analysis will be done at enrollment, 4.5 mos and 9 mos, for both groups. We plan to account for dietary intakes of protein, sodium, calcium, and phosphorous on BMD. Each participant will turn in dietary logs of 3-days per week on a weekly basis. The dietary log of each participant will be analyzed by our registered dietitian using Nutrition Data System for Research (NDSR) software. We will solicit the service of our dietitian who will contact participants once a month to advise them on balanced diet. Additionally, the World Health Organization quality of life (WHO-QOL) survey will be used to assess participants' physical and mental domains after intervention. The WHO-QOL is a survey instrument that rates six broad domains on health (physical, psychological, level of independence, social relations, environment, and spirituality/religion/personal belief), using a five-point Likert scale (1-5) to produce a total of 100 items in assessment. This survey will be administered at enrollment and at the end of intervention. It takes about 15 minutes to complete the survey. Data obtained from the survey will serve as preliminary data to determine whether exercise programs could also enhance the QOL for persons with SCI. It will be interesting to note any association between physical domain and bone parameters after SCI.

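### Drugs that act directly on bone appear in neither exclusion list, and the supplied text specifies no record of their use at baseline or of starts during the 9 months

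*Combined protocol and SAP*

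**What the plan says.** The Exclusion Criteria under Research Design and Methods close with the purpose of the list: "We have chosen inclusion and exclusion criteria for this study, to optimize homogeneity". In keeping with that purpose, they remove postmenopausal and estrogen-deficient women and people with more advanced chronic kidney disease, and add that "men undergoing anti-androgen therapy or post orchiectomy, will be excluded". AIS C and D are left out because weight bearing may confound the result. The only drug-related exclusions there, and in the second list in the Human Subject Section, are anticoagulant or antiplatelet therapy, insulin and anti-androgen therapy.

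The Background and Rationale shows that the authors had bone-active drugs in view: "Anti-resorptive drugs (bisphosphonate and denosumab) and anabolics (PTH peptides), have been shown to reduce fracture risk at vertebral and hip sites". It also says that anti-sclerostin drugs raise bone formation, lower resorption and increase BMD. Aim 2 measures these same processes, noting that in able-bodied people "serum CTX and serum P1NP are considered the best markers of bone resorption and formation, respectively". Aim 1 measures bone structure by MRI and BMD by DXA.

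The study removal criteria do not mention starting a bone-active drug, and the Adverse Events section says that usual care continues throughout. The confounders named under Statistical Analyses are age, level of injury and time since injury. The Data Analysis Plan names one ANCOVA covariate, the baseline score. The monthly pill count covers vitamin D only.

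**The concern.** The plan controls several influences on bone (hormones, kidney disease, weight bearing, diet, fat mass) but leaves out the drugs whose purpose is to change bone. Followed as written, it can enrol current users and allows starts under usual care. The general clauses do not clearly close the gap: one excludes an active medical condition that may confound the result, which is not a drug, and the investigator's-judgment item concerns safety and infection risk.

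What is at stake is the effect-size estimate. The Sample Size Justification says that the pilot serves to give preliminary evidence and an effect size for a larger trial. Drug effects on CTX, P1NP or BMD that are neither kept out nor described would widen that estimate or, for starts after randomisation, could shift it.

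**Working it through.** **Inputs from the documents.** Sample Size Justification: "The proposed sample size of 10 per group is adjudged sufficient to accomplish these goals", and "we will have 80% power to detect a standardized mean difference of" d = 0.9 at alpha 0.25, sidedness not stated. Recruitment plan: 10 in the "intervention group vs. 10 in control group". Data Analysis Plan: ANCOVA on the baseline score.

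**Inputs assumed.** The documents give neither the prevalence of use nor the size of a drug effect. Prevalence p is taken from 2% to 30%. The drug effect g is 1 SD for baseline use, and 0.5 to 1.5 SD for starts.

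**1. The plan's own power.** With 10 per arm, d = 0.9 and two-sided alpha 0.25, the noncentrality is 0.9 × √(10/2) = 2.01. Power is 80.6% by the normal approximation and 79.6% by the noncentral t with 18 df. One-sided alpha 0.25 would give about 91%. The stated 80% therefore reproduces as a two-sided figure.

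**2. Use at baseline.** Treat the users in each arm as independent Binomial(10, p) counts. A user's outcome is shifted by g, so the outcome SD is multiplied by √(1 + p(1 − p)g²) and the effective d is 0.9 divided by that factor. With g = 1:

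| p | Chance arms differ by 2 or more users | SD factor | Effective d | Power |
|---|---|---|---|---|
| 2% | 3% | 1.010 | 0.891 | 79.1% |
| 5% | 11% | 1.023 | 0.879 | 78.3% |
| 10% | 24% | 1.044 | 0.862 | 77.2% |
| 20% | 39% | 1.077 | 0.836 | 75.4% |
| 30% | 46% | 1.100 | 0.818 | 74.2% |

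At 20% use, √(1 + 0.2 × 0.8) = 1.077, an 8% rise in SD, and 0.9/1.077 = 0.836.

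A two-user difference moves the contrast by (2/10) × 1 = 0.2 SD. The standard error of the contrast is √(2/10) = 0.45 SD, so the shift is 0.2/0.45, under half a standard error. Under randomisation this is part of sampling variation, not an added bias. These figures also ignore baseline adjustment, which removes part of the effect of stable use, so they are upper-end for that case.

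**3. Starts after randomisation.** If one arm has k more starters than the other, the contrast moves by (k/10) × g.

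| Extra starters k | g = 0.5 | g = 1 | g = 1.5 |
|---|---|---|---|
| 1 | 0.05 SD | 0.10 SD | 0.15 SD |
| 2 | 0.10 SD | 0.20 SD | 0.30 SD |

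For k = 2 this is 11% to 33% of d = 0.9 (0.10/0.9 to 0.30/0.9). At k = 2 and g = 1, power falls to 65.4% if the extra starters are controls and the drug acts in the same direction as the intervention. With no true effect, the chance of a nominally significant result rises from 25% to 29.4%. These figures are conditional on that imbalance and on the full drug effect being present by the measurement, so they too are upper-end. If both arms start at the same rate, starts are again noise. They become a systematic shift only if the rates differ by arm, which randomisation does not rule out once treatment has begun.

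**The case against.** A reader might infer that use of these drugs goes unrecorded. The documents do not support that. Sources of Materials provides for review of the medical record, Study Procedures for a history at screening, and the contents list an Appendix 2 of common data elements that is not in the supplied text. What can be said is that the supplied text specifies no such record.

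A reader might also infer that chance imbalance in 10 per arm could hide the effect or create one. That is too strong. Imbalance at baseline is already in the standard error, and under the assumptions above it costs a few points of power.

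Other criteria already remove many likely users: severe osteoporosis, total body T-score below −2.5, knee BMD below 0.6 g/cm², age over 65, and postmenopausal women. This also makes it less likely that the baseline DXA would prompt a start, because people with the lowest values are not enrolled. These rules do not reach a treated person whose values lie above the cut-offs.

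The 1 SD effect has no support in the documents. The Background notes a lack of consensus on fracture benefit at the femur and says that anti-sclerostin use in SCI is still under study.

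Finally, this is a pilot with mainly descriptive analysis, and small, heterogeneous samples are an acknowledged pitfall. All of this limits the size of the point. It does not supply the missing eligibility line or log.

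**Conclusion.** The gap stands as a low-cost improvement, not a threat to the trial. Eligibility rules written for homogeneity pass over drugs that the Background itself describes as acting on bone, and the supplied text specifies no record of their use or of starts.

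For use at baseline the consequence is mainly extra noise: an 11% to 39% chance of a difference of two or more users at 5% to 20% use, and power of about 75% instead of 80% at 20% use with a 1 SD effect, before the partial correction from ANCOVA. For starts after randomisation the baseline covariate gives no correction. Each extra starter in one arm moves the contrast by one tenth of the drug effect, so partial distortion of the effect-size estimate is the realistic risk. Wholly creating or erasing d = 0.9 is not.

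Prevalence, drug effect and start rates are all assumptions. If use is near 2%, little is lost.

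**What to change.** 1. Add current or recent use of bone-active drugs to both exclusion lists, in matching words. The sponsor's clinicians should set which drugs count and the look-back window.
2. Record such use at baseline, ask about any start at the existing monthly calls, and report both by arm.
3. Keep all randomised participants in the main analysis. Show a sensitivity analysis for on-study starters only beside it. Aim 1 imaging has one post-baseline scan, at 9 months, so setting aside results after a start drops that participant after randomisation, from an arm of 10.

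The cost is one eligibility line, one log item and one extra analysis, plus a somewhat smaller pool. The registry figure of more than 298 is not the eligible pool: it counts injury level, or level with AIS grade, before the caregiver, ECG, implant, anticoagulant and BMD criteria. The plan already allows for failing to find 20 Veterans. If recruitment is at risk, recording use and reporting it by arm, without the exclusion, keeps much of the benefit.
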